3.2 DISCUSSION OF STUDY DESIGN

While the prognosis of MDS patients who are refractory to or have relapsed after treatment with hypomethylating agents is universally poor. For higher risk MDS patients, overall survival is extremely short, with estimates ranging from 3-6 months. Therefore, for this group, the primary endpoint is doubling of overall survival from 6 to12 months. The tosedostat dose of 120 mg per day for this study was chosen based safety, efficacy and convenience established in the prior studies CHR-2797-002 and OPAL. Based on preliminary clinical and in vitro data, it is possible that tosedostat may synergize with and/or restore sensitivity to the hypomethylating agent azacitidine. Therefore, for patients who have stable disease, but no hematological improvement after 2 cycles with tosedostat, the investigator may add azacitidine 75 mg/m² IV or SC for 5 days to tosedostat.

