8 STATISTICS

This is an open-label, phase II study designed to explore the clinical activity of tosedostat in patients with MDS who have failed therapy with hypomethylating agents. The study will include 80 patients with high and very high risk MDS with the goal of doubling median overall survival from 6 to 12 months. A futility analysis will be performed after the first 40 patients are treated, and if the median overall survival is less than 3 months, then we will consider closing the study.

Sample size considerations:

The primary endpoint for is overall survival, as measured from the start of the treatment to the date of death (or date of last follow-up if no death). Previous data suggest that the median overall survival for high risk MDS patients is 6.0 months. With the administration of tosedostat, we anticipate the median overall survival to be improved to ≥ 9 months. A sample size of 80 patients is planned for this study, which will give us at least 85% power to detect the hypothesized improvement. This calculation assumes a Type I error of 10%, a one-sided test, and a median follow-up time of 2.5 years. It also assumes that survival times are exponentially distributed. This last assumption is for planning purposes only; actual analysis will employ nonparametric methods for estimation and testing of survival distributions. A two-sided 95% confidence interval for the median overall survival is estimated to be (6.2 months, 12.7 months) under the hypothesized improvement. At an accrual rate of 3-4 patients per month, we anticipate to complete enrollment in approximately two years.

Analysis Plan:

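### Section 3.2 words the primary endpoint as a doubling of median survival to 12 months, but the 80 patients, the power and the expected interval are planned on 9 months, and no rule says which value governs

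*Combined protocol and SAP*

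**What the plan says.** Two target values are attached to overall survival (OS).

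- **12 months.** Section 3.2 states that "the primary endpoint is doubling of overall survival from 6 to12 months". The first paragraph of Section 8 describes 80 patients "with the goal of doubling median overall survival from 6 to 12 months".
- **9 months.** Under the sample size considerations in Section 8, the reference is that "the median overall survival for high risk MDS patients is 6.0 months", and then "we anticipate the median overall survival to be improved to ≥ 9 months". The power statement follows from that: "A sample size of 80 patients is planned for this study, which will give us at least 85% power to detect the hypothesized improvement". Its conditions are given as "This calculation assumes a Type I error of 10%, a one-sided test, and a median follow-up time of 2.5 years" and "It also assumes that survival times are exponentially distributed". The same paragraph expects a two-sided 95% confidence interval of 6.2 to 12.7 months for the median if the hypothesized improvement is true.

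The synopsis, Section 2 and Section 3.1.4 name the primary endpoint as overall survival and give no target value. No section calls one figure a minimum and the other an aspiration. No section says which observed median, or which test result against 6 months, would make the trial positive.

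**The concern.** A doubling (6 to 12 months) and a 1.5-fold gain (6 to 9 months) are different effects. Section 3.2 makes the larger one part of the endpoint, while Section 8 sizes the trial on the smaller one. A drug that performs exactly as the sample size paragraph supposes would usually miss the endpoint as Section 3.2 words it.

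The study is open-label and describes no control group, so the observed median is likely to be the headline result. If it lands between the two values, nothing written in advance tells the reader how to judge it, and the yardstick could be picked once the data are known.

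**Working it through.** **Inputs.** From Section 8: N = 80, reference median 6.0 months, planned median 9 months, one-sided alpha 10%, exponential survival, median follow-up 2.5 years. From Section 3.2 and the opening of Section 8: alternative target 12 months. From Section 4.3: enrollment over about 24 months, total duration about 36-48 months. The plan names no test for the power calculation, so three candidates were tried.

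**Step 1: the stated figures at 9 months.**

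- *Test of 6-month survival, normal approximation.* S(6) is 0.500 under the reference and 0.5^(6/9) = 0.630 under the alternative. Critical value: 0.5 + 1.2816 × √(0.25/80) = 0.5716. Standard error under the alternative: √(0.630 × 0.370/80) = 0.0540. Power = Φ((0.6300 − 0.5716)/0.0540) = Φ(1.08) = 86.0%. For 85% power, n = 77.1, so 78.
- *Kaplan-Meier (KM) median, log scale.* The standard error is 1/(√80 × ln 2). Power = Φ(ln 1.5 × √80 × ln 2 − 1.2816) = Φ(2.514 − 1.282) = 89.1%.
- *Exponential log-hazard test, 30 months of follow-up for everyone (assumed).* Events = 80 × (1 − 0.5^(30/9)) = 72. Power = Φ(√72.06 × ln 1.5 − 1.2816) = 98.5%.
- *Expected interval.* The 95% limits for a median with n = 80 are about the 31st and 50th ordered times, placed at −ln(1 − k/81) × 9/ln 2. This gives 6.26 and 12.47 months, against the stated 6.2 and 12.7.

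The statement of at least 85% power and the interval are both recovered at 9 months.

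**Step 2: the same formulas at 12 months.**

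| | Planned median 9 | Planned median 12 |
|---|---|---|
| S(6) under the alternative | 0.630 | 0.707 |
| Power, 6-month survival test | 86.0% | 99.6% |
| Power, KM median | 89.1% | 99.9% |
| n for 85% power, 6-month survival test | 78 | 29 |
| n for 85% power, KM median | 69 | 24 |
| Expected 95% interval (months) | 6.3 to 12.5 | 8.4 to 16.6 |

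Other standard interval formulas move the ends by a few tenths of a month, which does not close the gap between the columns. The stated N, power and interval belong to 9 months.

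**Step 3: where the two targets disagree.** An observed median of 12 or more satisfies both. From 9 to just under 12 it meets the planning target and misses the doubling. The test against 6 months rejects lower still: for the KM median at one-sided 10%, from 6 × exp(1.2816/(√80 × ln 2)) = 7.4 months.

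**Step 4: how often that happens if the true median is 9.** Simulated with N = 80, exponential survival, uniform 24-month accrual and a cut at 36 or 48 months. The stated median follow-up of 2.5 years corresponds to a cut near 30 + 12 = 42 months, between the two.

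- Observed median of 12 or more: about 2-3% of trials.
- Observed median from 9 to just under 12: about 43-47%. The spread is mainly the convention for reading a median off the KM curve.
- Rejecting 6 months while the observed median is below 12:

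| Test | One-sided 10% | Two-sided 0.05 |
|---|---|---|
| 6-month survival | about 85% | about 65% |
| KM median | about 84% | about 65% |
| One-sample log-rank | about 95-96% | about 89-91% |

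The second alpha is included because the analysis plan in Section 8 evaluates p-values two-sided at 0.05.

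**The case against.** The strongest reply is that neither number is a decision threshold. The synopsis and Sections 2 and 3.1.4 state the endpoint as overall survival alone, and Section 8 defines it as time from start of treatment to death. In Section 8, 12 months is a goal and 9 months an anticipated effect for sizing. Only one sentence, in the narrative of Section 3.2, ties the word endpoint to doubling. Because the sizing value is written as at least 9, a hoped-for 12 lies inside it, and the pair could be a minimum effect and an ambition.

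Much of this stands. A reader might infer that one survival result would be declared both a success and a failure. The documents do not support that, because they contain no success rule that could produce either verdict. A reader might also take about 96% as the chance of a significant result that misses doubling. That is the top of a range of about 65% to 96%, set by a choice of test and alpha that the plan leaves open. Nor does it count as evidence that about half of trials would observe less than 12 months if the true median were 12: that holds for any threshold placed at the true value.

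What does not stand is that the wording reconciles itself. No section labels the values as minimum and ambition, Section 3.2 does make the doubling the endpoint, and the planning figures reproduce at 9 and not at 12.

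**Conclusion.** The inconsistency is real and unresolved: the endpoint as worded in Section 3.2 carries a target of 12 months, while the trial is sized for 9. The effect is confined to observed medians below 12 months, and is clearest from 9 to just under 12. If the drug performs as planned, that band holds about 43-47% of trials, and a median of 12 or more occurs in about 2-3%. These frequencies assume exponential survival, uniform 24-month accrual and a cut at 36 or 48 months.

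The sample size, the stated power at 9 months and the 3-month futility criterion are unaffected. The fault lies in how the result would be judged, and the lack of any stated success rule leaves that open.

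**What to change.** In Section 3.2 and the first paragraph of Section 8, replace the doubling from 6 to 12 months with the effect the trial was planned on: median OS improved from 6 to 9 months. Keep the primary endpoint as overall survival from start of treatment.

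Add one sentence saying that the conclusion rests on a prespecified test of OS against a 6.0-month median, naming the test and its alpha, and not on whether the observed median reaches 9 or 12. Swapping 12 for 9 alone would not be enough, since medians between about 7.4 and 9 months would stay ambiguous. Twelve months may remain as an aspiration with no part in the conclusion.

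Naming the alpha also means choosing between the one-sided 10% of the planning and the two-sided 0.05 of the analysis plan. That is a separate question, but not a neutral one: at two-sided 0.05 the power at 9 months is 64.7% (6-month survival), 71.0% (KM median) or 93.1% (exponential test).

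The cost is a few sentences of protocol text, with no change to N or procedures. The downside is that the stated ambition becomes smaller.

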4 SELECTION OF STUDY POPULATION

4.1 INCLUSION CRITERIA

Male and female MDS patients who meet all of the following criteria are eligible for enrollment in the trial:

1. Able to understand and to provide written informed consent
2. At least 18 years of age with pathologically confirmed MDS (IPSS-R high or very high) or 20-30% blasts in bone marrow per FAB classification (RAEB-T)
3. Must have received at least 4 cycles of decitabine-based or azacitidine-based therapy and are either refractory to, relapsed after or intolerant to prior therapy with either agent.
 - *Primary failure/refractory:* Stable or worsening disease after a minimum of 4 cycles of decitabine-based or azacitidine-based therapy
 - *Secondary failure/relapse:* Bone marrow blast count increase or loss of hematologic response after initial treatment response with hypomethylating agent-based therapy
 - *Intolerance:* Intolerance of hypomethylating agent-based therapy regardless of number of cycles completed and clinical response
4. Progression (according to 2006 IWG criteria) at any time after initiation of subcutaneous or intravenous azacitidine or decitabine treatment per labeling during the past 2 years, defined as follows:
 - For patients with <5% BMBL, ≥ 50% increase in BMBL to >5% BMBL
 - For patients with 5-10% BMBL, ≥ 50% increase in BMBL to >10% BMBL
 - For patients with 10-20% BMBL, ≥ 50% increase in BMBL to >20% BMBL
 - For patients with 20-30% BMBL, ≥ 50% increase in BMBL to >30% BMBL
 - Any of the following:
 - ≥ 50% decrease from maximum remission/response levels in granulocytes or PLT

- Decrease in Hgb concentration by ≥ 2 g/dL
- Transfusion dependence, defined as administration of at least 4 RBC units in the past 8 weeks before Screening (patients must have Hgb values < 9 g/dL prior to transfusion to be considered), in the absence of another explanation.

5. Has failed to respond to, relapsed following, not eligible, or opted not to participate in BM transplantation
6. Off azacitidine or decitabine for at least 2 weeks, off all other anticancer treatments for at least 2 weeks. Filgrastim (G-CSF) and EPO are allowed before and during the study as clinically indicated
7. Eastern Cooperative Oncology Group (ECOG) performance status of 0-3
8. Subjects must have adequate hepatic and renal function including the following:
 - Total bilirubin $\leq 1.5 \times$ upper limit of normal (in the absence of Gilbert's syndrome)
 - AST and ALT $\leq 2.5 \times$ upper limit of normal
 - Serum creatinine $\leq 1.5 \times$ upper limit of normal
9. Must have acceptable recovery from clinically significant non-hematologic toxicity after prior therapy.
10. Must have a life expectancy of at least 2 months
11. Screening left ventricular ejection fraction (LVEF) $> 50\%$ as documented by transthoracic echocardiogram (TTE)
12. Female subject of child-bearing potential and male subjects with female partners of reproductive potential must use acceptable contraceptive methods (hormonal or barrier method of birth control; abstinence) for the duration of time on study and continue to do so for a further 3 months after the end of tosedostat treatment. Should a female subject become pregnant or suspect she is pregnant while participating in this study, she should inform her treating physician immediately.
13. Able to comply with all study procedures during the study including all visits and tests
14. Willing to adhere to the prohibitions and restrictions specified in this protocol
15. Patient must sign an informed consent form (ICF) indicating that s/he understands the purpose of and procedures required for the study and is willing to participate.

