3.1.4 Clinical Study Endpoints

The primary endpoint the study is to evaluate the safety and efficacy of tosedostat in patients with myelodysplastic syndrome who have relapsed after or are refractory or intolerant to azacitidine or decitabine. The primary endpoint for patients is overall survival.

The following secondary endpoints will be evaluated:

- Hematological improvements (erythroid response [ER], platelet response [PLR] and neutrophil response [NR]) according to 2006 IWG criteria (Appendix 2), including reduction in RBC and/or PLT transfusion needs
- Overall response (complete remission [CR], partial remission [PR], bone marrow complete response [BMCR], and stable disease [SD] according to 2006 International Working Group (IWG) criteria, including, among responders, the distribution of time to response and the duration of response (Appendix 2). All responses of CR must be confirmed 4 weeks after achievement.
- Improvements of cytogenetics as evaluated by the change in aneuploidy in BM according to 2006 IWG criteria
- Safety and tolerability of tosedostat

- Time to AML transformation

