5.2.3 Even Cycles Day 28

Response to be assessed through examination of bone marrow and peripheral blood according to the 2006 IWG criteria.²⁰

- Collect samples for local laboratory evaluation for hematology
- Bone marrow aspiration and/or biopsy for confirmation of response
- Record concomitant medications
- Assess and record AEs

Patients with noted responses of CR or PR must have their responses confirmed 4 weeks after initial documentation of response. Patients with noted responses of hematologic improvement at the end of Cycle 2 must have their responses confirmed 8 weeks after initial documentation of response.

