5.7.4 Criteria for Protocol-Defined Required Discontinuation of Treatment

- Discontinue treatment with tosedostat if patients experience any of the following:
- Do not achieve CR, PR, hematologic improvement, or bone marrow remission after four cycles of treatment with tosedostat alone or 4 cycles of azacitidine if azacitidine is added to tosedostat.
- Experience disease progression
- Develop an intercurrent illness that prevents further treatment with tosedostat
- Develop unacceptable/intolerable AE(s)
- Withdraw from the clinical study
- Become pregnant
- Receive other systemic cancer therapy or protocol-prohibited medications
- Have general or specific changes that render the patient unsuitable for further treatment with tosedostat, in the judgment of the Investigator

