6.6.2 Allowed Medications

The following medications may be used within the recommendations of nationally applicable marketing approvals and the following limits:

- Anticoagulant Therapy: subjects who are taking warfarin (or equivalent) may participate in this study; however, it is recommended that prothrombin time (PT) be monitored carefully at least twice per week for the first month, followed by the pre-study level of monitoring if the international normalized ratio is stable. Subcutaneous heparin is permitted

- Colony Stimulating Factors: the routine use of granulocyte colony stimulating factors (GCSFs or GM-CSFs) is permitted for the treatment of neutropenic sepsis during this study. Subjects should not receive G-CSFs prophylactically in general.
- When use of concomitant medications with QT-prolonging potential is necessary, ECG must be repeated 4 hours post-dose on Day 1 (+1 day), on Day 3 (± 1 day), and on Day 7 (± 1 day), and as clinically indicated, relative to start of agent with QT-prolonging potential. QTc will be calculated using the Fridericia formula.

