Survival	
Endpoints:
 
 • Overall: death from any cause • Event free: failure or death from any cause • PFS: disease progression or death from MDS • DFS: time to relapse • Cause-specific death: death related to MDS

IWG response criteria for hematologic improvement²⁰

Hematologic improvement*	Response criteria (responses must last at least 8 wk)
Erythroid response (pretreatment, < 11 g/dL)	Hgb increase by ≥ 1.5 g/dL
	Relevant reduction of units of RBC transfusions by an absolute number of at least 4 RBC transfusions/8 wk compared with the pretreatment transfusion number in the previous 8 wk. Only RBC transfusions given for a Hgb of ≤ 9.0 g/dL pretreatment will count in the RBC transfusion response evaluation [†]
Platelet response (pretreatment, $< 100 \times 10^9/L$)	
Absolute increase of $\geq 30 \times 10^9/L$ for patients starting with $> 20 \times 10^9/L$ platelets
 
Increase from $< 20 \times 10^9/L$ to $> 20 \times 10^9/L$ and by at least 100%[‡]

Neutrophil response (pretreatment, $< 1.0 \times 10^9/L$)	At least 100% increase and an absolute increase $> 0.5 \times 10^9/L$ [‡]
Progression or relapse after HI	
At least 1 of the following:
 
 • At least 50% decrement from maximum response levels in granulocytes or platelets • Reduction in Hgb by ≥ 1.5 g/dL • Transfusion dependence

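### Growth factors allowed on study can inflate erythroid, and less often neutrophil, response, because neither the visible response criteria nor Section 8 says how to handle them

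*Combined protocol and SAP*

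**What the plan says.** Section 4.1, criterion 6, says "Filgrastim (G-CSF) and EPO are allowed before and during the study as clinically indicated". The synopsis carries the same text.

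Section 6.6.2 says "the routine use of granulocyte colony stimulating factors (GCSFs or GM-CSFs) is permitted for the treatment of neutropenic sepsis during this study" and adds "Subjects should not receive G-CSFs prophylactically in general". It does not mention EPO.

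Section 3.1.4 lists hematologic improvement (erythroid, platelet and neutrophil response, including reduced transfusion need) first among the secondary endpoints. In Appendix 2:

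- Erythroid response is a hemoglobin rise of 1.5 g/dL or more, or at least 4 fewer red-cell transfusions per 8 weeks.
- Neutrophil response is "At least 100% increase and an absolute increase" above 0.5 x 10^9/L.
- Both must last 8 weeks. Section 5.2.3 adds that an improvement seen at the end of Cycle 2 "must have their responses confirmed 8 weeks after initial documentation of response".
- CR, which must last 4 weeks, needs hemoglobin of at least 11 g/dL and neutrophils of at least 1.0 x 10^9/L. PR carries these over if they were abnormal before treatment.

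No growth-factor condition appears in the visible criteria. Section 8 has no stable-dose, non-evaluable or sensitivity rule for growth factors. Section 6.6 does require concomitant drugs to be recorded with dose regimen, indication and dates.

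**The concern.** EPO and G-CSF act on the counts that define two of the three hematologic improvement components. The protocol's own background lists erythropoietin and colony-stimulating factors as supportive treatment in MDS, and it cites a decision model for treating MDS anemia with erythropoietin plus G-CSF. A patient who starts EPO in Cycle 1 and then needs fewer transfusions would count as an erythroid responder to tosedostat. In a single-arm trial, no comparison group shows how often that would have happened anyway.

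The affected results are the hematologic improvement rate, the transfusion independence comparisons planned in Section 8, and in part CR and PR. Hematologic improvement also steers treatment. Under Section 5.7.4, tosedostat stops for patients who "Do not achieve CR, PR, hematologic improvement, or bone marrow remission after four cycles". Under Section 3.2, stable disease without improvement after two cycles opens the azacitidine add-on.

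**Working it through.** **The plan's own figure.** The plan gives no rate, threshold or power for hematologic improvement. Its only power figure is for overall survival (Section 8): N = 80, median 6 versus 9 months, one-sided 10%, follow-up 2.5 years, at least 85% power.

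- Deaths, giving every patient 30 months of follow-up: 80 x (1 - exp(-ln2 x 30/9)) = 72.1.
- SE of the log median: 1/(sqrt(72) x ln2) = 0.170.
- Power: Phi(ln1.5/0.170 - 1.2816) = 86.5%.

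The stated figure is reproduced, and nothing in it depends on growth factors.

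**Which components are exposed.**

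- Erythroid response: exposed. No visible text limits starting or increasing EPO on study, and continued EPO can span the 8 weeks.
- Neutrophil response: less exposed. A short G-CSF course for sepsis is unlikely to sustain a doubling for 8 weeks. Criterion 6, read alone, allows wider use.
- Platelet response: not directly affected by either drug.
- CR and PR: only the hemoglobin and neutrophil thresholds are exposed. CR also needs at most 5% marrow myeloblasts, no blood blasts and platelets of at least 100 x 10^9/L. PR needs marrow blasts to fall by at least half.

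**Illustrative size.** Let p be the true improvement rate and g the share of patients who start or increase a growth factor after baseline. Let r be the chance that this alone meets a response rule. All three are assumptions; the documents give none of them. Then:

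observed rate = p + (1 - p) x g x r

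- g = 0: no inflation.
- Smallest case in the grid (p = 20%, g = 10%, r = 10%): 0.80 x 0.01 = 0.8 points, or 0.6 of 80 patients.
- Middle case (p = 10%, g = 20%, r = 20%): 0.10 + 0.90 x 0.04 = 13.6%, which is +3.6 points or 2.9 patients.
- Largest case (p = 0, g = 40%, r = 40%): 16.0 points, or 12.8 patients.

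For scale, the exact 95% interval for 8 of 80 is 4.4% to 18.8%. At p = 10% the middle case (13.6%) lies inside it. The case g = r = 40% gives 0.10 + 0.90 x 0.16 = 24.4%, which lies outside.

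**The case against.** **The footnotes may contain a rule.** Appendix 2 carries footnote marks on the hematologic improvement heading and on the red-cell transfusion and neutrophil lines, and their text was not available here. A growth-factor condition there cannot be ruled out, so this stands as a limit on the point. Section 8 is silent either way.

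**The bias is not shown.** A reader might infer that hematologic improvement is biased upward as a whole. The documents do not support that. Upward bias needs a start or increase after baseline. Stable prior use is already in the pretreatment value and adds little, and stopping prior use could push the rate down. Platelet response is outside the mechanism, and the 8-week rule blunts short G-CSF courses. All of this stands, but the 8-week rule does not protect against continued EPO.

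**G-CSF is restricted.** A reader of criterion 6 alone might conclude that G-CSF is freely allowed. Section 6.6.2 says otherwise. The narrower section might be taken to govern, but nothing in the protocol says so.

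**CR and PR need more than blood counts.** This is correct. These drugs do not explain the marrow requirements, so only part of each definition is exposed.

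**Changing the criteria would change treatment.** This is also correct. Hematologic improvement feeds Sections 5.7.4 and 3.2, so rewriting Appendix 2 would alter who must stop and who may receive azacitidine. Voiding every neutrophil response with any G-CSF in the window would also discard genuine responses after a single sepsis course.

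**The endpoint is secondary and descriptive.** This is true, and it limits the weight of the point. It does not make the reported rate interpretable.

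**Conclusion.** The point holds as a gap in the analysis plan. Criterion 6 and Section 6.6.2 differ on G-CSF, and neither limits EPO. As far as the visible text shows, a growth factor started or increased on study can produce an erythroid response, and less often a neutrophil response, that is credited to tosedostat. The design offers no way to separate the two effects.

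The size cannot be determined from the documents. It is zero if nobody starts or escalates. It is about 1 to 13 extra responders of 80 across the grid of p = 0 to 20% and g and r each 10 to 40%, all assumed values. The primary endpoint, its sample size and platelet response are unaffected.

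**What to change.** - In Section 8, pre-specify that erythroid response, and the hemoglobin part of CR and PR, is reported as attributable to tosedostat only if EPO was not started or increased in the response window. Apply the same rule to neutrophil response, and the neutrophil part of CR and PR, for G-CSF.
- Define the window so that it runs from the pretreatment value through the required duration (8 weeks for hematologic improvement, 4 weeks for CR and PR). Otherwise a start between baseline and first documentation would be missed.
- Report each rate with and without the restriction.
- Leave the Appendix 2 criteria used for continuation and azacitidine add-on decisions unchanged, and check their footnotes for any existing growth-factor condition.
- Reconcile criterion 6 (Section 4.1 and synopsis) with Section 6.6.2, including what is intended for EPO.

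The cost is analysis wording plus the reconciliation. The dates and doses are already recorded under Section 6.6, and the sample size does not change. The downside is slightly fewer counted responders in the restricted rate.
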